4.2 Secondary Endpoints

- Time from randomisation to start of next line of systemic therapy or clinical decision that patient not suitable for further systemic therapy as determined by the treating physician, or death.
- Overall survival time from randomisation until death from any cause

HALT Protocol

- Patterns of disease progression identified from CT scans / PET-CT scans taken at 3 monthly intervals to further document natural history of oncogene-addicted NSCLC
- Radiotherapy toxicities (acute and late) assessed using CTCAE v4.0 (clinician and patient versions where available). Acute events are defined as ≤ 90 days post SBRT start date (applicable for each subsequent course of SBRT where relevant) and late events are defined as > 90 days, both assessed using CTCAE v4.0.
- Quality of Life assessed using EQ-5D-5L and the EORTC QLQ-C30
- Measurement of resistant sub-clones in ctDNA measured at baseline, post-randomisation and upon progression.
- Time to failure of next line treatment time from randomisation to switch from next line of active systemic therapy.

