12.1 Definitions

Adverse Event (AE)

An AE is any untoward medical occurrence in a patient administered a study treatment; the event does not necessarily have a causal relationship with the treatment.

For the purpose of this trial, any detrimental change in the patient's condition subsequent to the start of the trial (i.e. randomisation) and during the follow-up period should be considered as an AE, in the opinion of the Chief Investigator.

Serious Adverse Event (SAE)

An SAE is any untoward medical occurrence that occurs after randomisation and within the following 140 days and:

- results in death,
- is life-threatening
- requires hospitalisation or prolongation of existing inpatients' hospitalisation
- results in persistent or significant disability or incapacity
- is a congenital anomaly or birth defect

For repeat SBRT treatment (where applicable) any untoward medical occurrence that occurs within 90 days of the last fraction of subsequent SBRT and fulfils one of the criteria above should be reported according to serious adverse event reporting timelines.

In addition, any radiotherapy grade \geq 4 events occurring between 140 days and 1 year after randomisation or 90 days and 1 year after any repeat SBRT should be reported according to serious adverse event reporting timelines.

Important adverse events that are not immediately life-threatening or do not result in death or hospitalisation but may jeopardise the subject or may require intervention to prevent one of the other outcomes listed in the definition above, may also be considered serious.

Progression of the indicated disease and death due to progression of the indicated disease are not considered SAEs.

Pregnancy or aid in the conception of a child whilst participating in a trial is not itself considered an SAE but should be followed up for congenital anomalies or birth defects.

Serious Adverse Reaction (SAR)

A serious adverse reaction is an SAE that is suspected as having a causal relationship to the SBRT treatment, as assessed by the investigator responsible for the care of the patient. A suspected causal relationship is defined as possibly, probably or definitely related (see definitions of causality table).

ity
Description
There is no evidence of any causal relationship with the trial treatment
There is little evidence to suggest there is a causal relationship (e.g. the event
did not occur within a reasonable time after administration of the trial

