12.2 Reporting Adverse Events to ICR-CTSU

For non-UK reporting requirements please see Appendix A7

Any toxicity, sign or symptom that occurs after randomisation which is not unequivocally due to progression of disease, should be considered an AE.

All AEs must be reported on the relevant electronic CRF and submitted to ICR-CTSU.

• Toxicity evaluation

The National Cancer Institute Common Terminology Criteria for Adverse Events (CTCAE) version 4 scoring criteria will be used for all toxicity assessments for patients randomised to both the treatment (SBRT) and control groups.

The severity of AEs should be graded according to the appropriate CTCAE criteria. For each AE, the highest grade observed since the last visit should be reported.

Whenever one or more toxicity/sign/symptom corresponds to a disease or a well-defined syndrome, only the main disease/syndrome should be reported.

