13.3 Statistical Analysis Plan

Analyses of efficacy will be according to the intention to treat principle. Time to event endpoints will be presented using Kaplan Meier survival plots and compared between treatment groups using the log-rank test. Hazard ratios will be derived from Cox proportional hazards models or methods such as restricted mean survival should the assumption of proportionality not be met. A planned subgroup analysis will explore treatment effect by mutation status (e.g. EGFR+ vs. other mutation), however it is recognised there is limited power to estimate these subgroup effects and thus analyses will be interpreted with the appropriate caution.

Patterns of further disease progression will be summarised by treatment group to document the natural history of oncogene-addicted lung disease.

Acute and late toxicity related to SBRT treatment, both physician and patient reported, will be analysed separately and summarised as frequencies and percentages at each time point with adjustment made for multiple testing. The proportion experiencing toxicity of any grade and grade \geq 3 will be presented and any comparisons made between randomised treatment groups using Fisher's exact tests. All safety analyses will use a safety population which will be pre-defined in the Statistical Analysis Plan.

Quality of life (QoL) data will be analysed using standard algorithms to derive scores and handle missing data according to the chosen questionnaire's scoring manual. Descriptive statistics (median, IQR, range) will be presented by treatment group at each timepoint. Analyses to account for the longitudinal nature of the data may also be used.

The integral translational work will include assessment of ctDNA clearance as a binary outcome with comparison between randomised treatment groups made using Fisher's exact tests. Logistic regression models will be used to adjust for any relevant baseline characteristics. Exploratory analyses

will look at the genetic relationship between baseline circulating biomarkers and archival tumour samples.

Further details of analysis methods will be specified in a Statistical Analysis Plan in accordance with ICR-CTSU Standard Operating Procedures.

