13.4 Interim Analyses and Stopping Rules

The TSC will monitor recruitment rate and may recommend trial closure if it is significantly lower than expected and continuation of the trial is deemed futile.

A futility analysis will be conducted after 50% of the PFS events have been recorded (49 PFS events, ~70 patients recruited). If the HR >1.0 then treatment with SBRT will be deemed futile. This analysis will contribute to the decision for continuation to phase III.

The IDMC will review emerging safety data. This will include a formal safety review after 10 patients recruited to SBRT given concurrently with background TKI have completed the 3 month follow-up visit to assess the impact of concurrent background TKI on radiotherapy toxicity and after 10 patients recruited to SBRT given sequentially with the background TKI have completed the 3 month follow-up visit to assess disease flare (defined as disease progression occurring between stopping background TKI and restarting background TKI following completion of (initial) SBRT treatment).

In all patients randomised to SBRT, consideration will be given to stopping the trial should the rate of grade 4/5 acute radiotherapy-related toxicity (defined as within 90 days of last treatment administration, including repeat SBRT treatment as applicable) be unacceptable (to be agreed by the TMG and IDMC a priori).

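### The toxicity outcome is framed as SBRT-related and dated from SBRT start, neither of which exists for controls, so the between-arm Fisher tests have no secured like-for-like outcome

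*Protocol*

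**What the plan says.** In the Protocol, the toxicity paragraph of section 13.3 opens with its subject: "Acute and late toxicity related to SBRT treatment, both physician and patient reported, will be analysed separately". These data are to be summarised at each time point, with an adjustment for multiple testing. The next sentence presents the proportions with any-grade and grade 3 or worse toxicity, with "any comparisons made between randomised treatment groups using Fisher's exact tests".

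Section 4.2 names the endpoint "Radiotherapy toxicities (acute and late) assessed using CTCAE v4.0" and dates it from radiotherapy: "Acute events are defined as ≤ 90 days post SBRT start date". The acute window restarts with each later SBRT course, and anything after 90 days is late.

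The causality wording in section 12.1 also points to SBRT: "A serious adverse reaction is an SAE that is suspected as having a causal relationship to the SBRT treatment". No section gives control patients a substitute start date or an equivalent causal category.

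The raw data are nevertheless collected in both arms. Section 12.2 says that the CTCAE "scoring criteria will be used for all toxicity assessments for patients randomised to both the treatment (SBRT) and control groups". Section 10.1 asks for a baseline CTCAE assessment in both arms, and section 10.3 times follow-up visits from randomisation for everyone.

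**The concern.** The safety question in a randomised comparison is how much toxicity SBRT adds to continued TKI. Only the control arm shows how much would have occurred anyway. A control patient cannot have SBRT-related toxicity, and without an SBRT start date an event in that patient is neither acute nor late as section 4.2 defines them.

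If the Fisher tests are applied to the outcome named at the head of the paragraph, part of any difference, or all of it, reflects attribution by sites that know the allocation. The total burden of toxicity could be identical in the two arms and the test could still reject. The primary analysis is not affected. What is at stake is whether a reported excess of toxicity, or a significance statement about it, can be read as harm caused by adding SBRT.

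**Working it through.** **The plan's own figures.** The Protocol gives no figure for the toxicity comparison, so there is none to reproduce. The only plan inputs are the arm sizes, 73 and 37 (section 5.1), which follow from 2:1 allocation of 110: 110 × 2/3 = 73.3 and 110 × 1/3 = 36.7.

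**Outcome and dating, side by side.**

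| Element | SBRT arm | Control arm |
|---|---|---|
| Related to SBRT (13.3) | Possible | Not possible |
| Day 0 for acute and late (4.2) | SBRT start, again for each course | None stated |
| CTCAE grade at common visits (10.1, 10.3, 12.2) | Yes | Yes |

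Section 11.2 asks for SBRT to start within 4 weeks of randomisation. The first acute window therefore closes between day 90 and day 28 + 90 = 118 after randomisation. Controls have no matching date.

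**Smallest count that reaches significance.** Two-sided Fisher tests of x/73 against 0/37:

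- x = 7 (9.6%): p = 0.093
- x = 8 (11.0%): p = 0.0496
- x = 10 (13.7%): p = 0.016

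Eight SBRT patients with attributed toxicity are enough.

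**Probability of rejecting when true toxicity is equal.** Assumptions, since the documents give none of these values: a proportion r of patients in each arm has toxicity of any cause, and in the SBRT arm a share s of those patients has it labelled SBRT-related. With 0/37 in controls, P(reject) = P(X ≥ 8), where X ~ Binomial(73, r × s). No multiplicity adjustment is applied.

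| r | s = 1/2 | s = 1/4 |
|---|---|---|
| 10% | 2.9% | below 0.1% |
| 15% | 18% | 0.6% |
| 20% | 45% | 2.9% |
| 30% | 87% | 18% |

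**Sensitivity to the zero.** If 10% of control toxicity were also labelled related, the s = 1/2 case would reject in 22% of trials at r = 20% and 42% at r = 30%.

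**Sensitivity to multiplicity.** Take, for illustration, Bonferroni over four tests (acute and late, any grade and grade 3 or worse), so the threshold is 0.05/4 = 0.0125. Then 11/73 (p = 0.0148) fails and 12/73 (p = 0.0077) passes, and P(reject) = P(X ≥ 12). For s = 1/2 this is 0.8%, 5.8% and 41% at r = 15%, 20% and 30%.

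**All-cause comparison.** With the same true rate in both arms and all toxicity counted from randomisation, Fisher's test at 73 v 37 rejects in 3.4% to 4.3% of trials for true rates of 10% to 70%. It holds its 5% level.

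**The case against.** The strongest reply is that the sentence carrying the Fisher test does not repeat the words about SBRT. It refers to toxicity by grade and is permissive ("any comparisons made between randomised treatment groups using" Fisher's exact tests). Routine adverse event reporting in section 12.2 asks for a CTCAE grade and mentions no causality field; the causality definitions in section 12.1 concern serious events. Summaries by time point work in both arms, because visits run from randomisation. Details such as a control reference date often sit in a statistical analysis plan.

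Much of this stands. A reader might infer that the protocol definitely commits to testing attributed counts against zero, or that it ignores control-arm toxicity. The documents support neither: an all-cause reading is open, the comparisons are optional, and control toxicity is collected and can be summarised visit by visit. A reader might also infer that sites attribute every routine adverse event to SBRT or not, which the text does not show.

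What remains is narrower. The paragraph's subject and the endpoint's name both point to the SBRT-related reading, and nothing secures the other. The acute and late split has no control anchor under either reading. The protocol itself fixes these definitions, so the point concerns what is stated and not what is left to a later plan. An optional comparison should still be valid if it is made.

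**Conclusion.** The point holds as a defect of definition. On the most direct reading, any between-arm test of the section 13.3 outcome compares an attributed rate with zero and can show a difference that is not extra harm.

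Its size cannot be fixed from the documents. Under the stated assumptions the distortion is negligible when toxicity is uncommon or seldom attributed (2.9% rejection at a 10% rate with half attributed, below the nominal 5%). It is severe when toxicity is common and often attributed (87% at a 30% rate with half attributed). Multiplicity adjustment reduces the rejection rates but leaves the contrast biased.

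It would go too far to say that a significant toxicity result in this trial must be an artefact, or that grade 3 or worse comparisons are necessarily inflated; at low rates they would not be. This is a secondary safety analysis, and neither the primary endpoint nor the sample size is touched.

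**What to change.** State in section 13.3 that comparisons between randomised groups use all-cause CTCAE toxicity, any grade and grade 3 or worse, as worst grade per patient. Count it from randomisation at the scheduled visits common to both arms: at 8 weeks, and cumulatively to the 5-month visit. Report SBRT-related acute and late toxicity by course, as a description of the SBRT arm only.

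The 140-day window used for serious events is less suitable. Toxicity is recorded as worst grade since the last visit, and the second visit falls at about day 56 + 91 = 147, after that window closes.

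In the same edit, reconcile the two acute windows. Section 4.2 counts from SBRT start, while section 13.4 has "defined as within 90 days of last treatment administration, including repeat SBRT treatment as applicable".

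The change is wording, using data already planned, and has two downsides:

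- Counting from randomisation includes up to 4 weeks before SBRT, which slightly dilutes an early effect.
- Routine toxicity visits stop at progression. With exponential PFS at the planning medians of 3 and 6 months, about 1 − 2^(−5/3) = 69% of controls and 1 − 2^(−5/6) = 44% of SBRT patients would have had a PFS event by month 5. Include the first post-progression toxicity assessment and report the numbers assessed by arm. Section 10.4 should make clear that its SBRT-only restriction applies to the 1-year assessment and not to this one.

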13.4 Interim Analyses and Stopping Rules

The TSC will monitor recruitment rate and may recommend trial closure if it is significantly lower than expected and continuation of the trial is deemed futile.

A futility analysis will be conducted after 50% of the PFS events have been recorded (49 PFS events, ~70 patients recruited). If the HR >1.0 then treatment with SBRT will be deemed futile. This analysis will contribute to the decision for continuation to phase III.

The IDMC will review emerging safety data. This will include a formal safety review after 10 patients recruited to SBRT given concurrently with background TKI have completed the 3 month follow-up visit to assess the impact of concurrent background TKI on radiotherapy toxicity and after 10 patients recruited to SBRT given sequentially with the background TKI have completed the 3 month follow-up visit to assess disease flare (defined as disease progression occurring between stopping background TKI and restarting background TKI following completion of (initial) SBRT treatment).

In all patients randomised to SBRT, consideration will be given to stopping the trial should the rate of grade 4/5 acute radiotherapy-related toxicity (defined as within 90 days of last treatment administration, including repeat SBRT treatment as applicable) be unacceptable (to be agreed by the TMG and IDMC a priori).

14 TRIAL MANAGEMENT

14.1 Trial Management Group (TMG)

The Trial Management Group (TMG) will include the Chief Investigator, ICR-CTSU Scientific Lead, Coinvestigators and identified collaborators, the Trial Statistician and Trial Manager. Principal Investigators and key study personnel will be invited to join the TMG as appropriate to ensure representation from a range of sites and professional groups. Where possible, membership will include a lay/consumer representative. The TMG will meet at regular intervals, and at least annually. Notwithstanding the legal obligations of the Sponsor and Chief Investigator, the TMG have operational responsibility for the conduct of the trial. The Committee's terms of reference, roles and responsibilities will be defined in a charter issued by ICR-CTSU.

14.2 Trial Steering Committee (TSC)

The Trial Steering Committee (TSC) will comprise an independent Chairman and at least two further independent members with clinical or statistical expertise (at least one member must be a statistician). The TSC will meet at regular intervals, and at least annually. The TSC will provide expert independent oversight of the trial on behalf of the Sponsor and funder. The Committee's terms of reference, roles and responsibilities will be defined in charter issued by ICR-CTSU.

14.3 Independent Data Monitoring Committee (IDMC)

The Independent Data Monitoring Committee (IDMC) will monitor the progress of the trial and will comprise a Chairman and at least two further members with clinical or statistical expertise (at least one member must be a statistician). Membership of the IDMC will be proposed by the CI, ICR-CTSU or wider TMG and endorsed by the TSC.

The IDMC will meet in confidence at regular intervals, and at least annually. A summary of findings and any recommendations will be produced following each meeting. This summary will be submitted to the TMG and TSC, and if required, the main REC and CRUK.

The IDMC will reserve the right to release any data on outcomes or side-effects through the TSC to the TMG (and if appropriate to participants) if it determines at any stage that the combined evidence from this and other studies justifies it.

The Committee's terms of reference, roles and responsibilities will be defined in a charter issued by ICR-CTSU.

15 RESEARCH GOVERNANCE

15.1 Sponsor Responsibilities

The Sponsor of this clinical trial is the Institute of Cancer Research (ICR). The Sponsor is responsible for securing the arrangements to initiate, manage and finance the trial.

A coordinating group in each participating (non-UK) country will be delegated responsibility for trial initiation and conduct in that country on behalf of the Sponsor, as defined in an agreement between the Sponsor and the coordinating group.

15.2 Participating Site Responsibilities

Responsibilities of participating sites are defined in an agreement between the individual participating site and the Sponsor (UK) or the coordinating group delegated that responsibility by the Sponsor (non-UK).

16 TRIAL ADMINISTRATION & LOGISTICS

16.1 Site activation

Before activating the trial, participating sites are required to sign an agreement accepting responsibility for all trial activity which takes place within their site.

Sites may commence recruitment once the site agreement has been signed by all required signatories, the required trial documentation is in place (as specified by ICR-CTSU) and a site initiation (visit or teleconference) has taken place. Sites will be notified via email when all requirements have been met and recruitment can commence. Site initiation visits will be conducted at sites where the Principal Investigator has requested one or where ICR-CTSU deems it is appropriate.

16.2 Investigator training

Each centre will be required to have completed the comprehensive pre-trial section of the quality assurance programme prior to commencing recruitment as detailed in the Radiotherapy Planning and Delivery Guidelines. To avoid duplication, every effort will be made to align quality assurance programmes with those of previous RTTQA approved trials (e.g. CORE) to minimise additional QA requirements. The radiotherapy QA programme will continue throughout the trial, with investigator training as required.

16.3 Data Acquisition

Electronic (e) Case Report Forms (CRF) will be used for the collection of trial data. ICR-CTSU will provide guidance to sites to aid the completion of the eCRFs. The Trial Management Group reserves the right to amend or add to the eCRF template as appropriate. Such changes do not constitute a protocol amendment and revised or additional forms should be used by sites in accordance with the guidelines provided by ICR-CTSU.

Data will be collected remotely from sites using the MACRO[®] database system and stored on ICR secure servers. Anonymised patient scans will be uploaded remotely onto the Institute's Research PACS (XNAT) system and stored on ICR secure servers.

16.4 Central Data Monitoring

Once data has been entered on the eCRF by the site personnel, ICR-CTSU will review it for compliance with the protocol and for inconsistent or missing data. Should any missing data or data anomalies be found, queries will be raised for resolution by the site.

Any systematic inconsistencies identified through central data monitoring may trigger an on-site monitoring visit.

16.5 On-Site Monitoring

If a monitoring visit is required, ICR-CTSU will contact the site to arrange the visit. Once a date has been confirmed, the site should ensure that full patient notes of participants selected for source data verification are available for monitoring along with access to eCRF data.

ICR-CTSU staff conducting on-site monitoring will review essential documentation and carry out source data verification to confirm compliance with the protocol. If any problems are detected during the course of the monitoring visit, ICR-CTSU will work with the Principal Investigator or delegated individual to resolve issues and determine appropriate action.

